Rapid deployment to remote mountainous regions will occur during MDO. Unacclimatized Service members experience altered carbohydrate metabolism, causing an increased reliance on glycogen for fuel, concomitant with a blunted ability to take up and oxidize exogenous carbohydrate. These negative physiological effects likely exacerbate declines in physical performance at HA. This proposal directly supports the Military Operational Medicine Research Program's Physiological Health and Performance Program Area under the Biomedical Performance Enhancement (BPE) Work Unit. Specifically, the proposed work aligns to BPE Strategic Plan's *Technical Objective 1.1.3: Material solutions (pharmacological) that enhance Soldier resistance to environmental stressors*.

This proposal will provide guidance for use of PIO to enhance exogenous carbohydrate oxidation at HA operations, and will provide the opportunity to determine if carbohydrate supplementation can indeed enhance performance if substrate metabolic dysregulation is avoided during HA exposure. Information from this proposal would be valuable to operational partners such as USSOCOM and the 10th Mountain Division who engage in HA MDO.

B4. OBJECTIVES/SPECIFIC AIMS/RESEARCH QUESTIONS

Objective:

1. Determine the effects of PIO on exogenous glucose oxidation and glucose turnover during exercise under acute HA exposure compared to PLA.
2. Determine the effects of PIO on inflammation during acute HA exposure compared to PLA.
3. Determine the effects of PIO on markers of iron status during acute HA exposure compared to PLA.

Hypotheses:

1. Exogenous glucose oxidation, Rd, and MCR during metabolically-matched, steady-state exercise at HA will be greater after PIO administration compared to PLA.
2. Inflammation will be lower during acute HA exposure after PIO administration compared to PLA.
3. Markers of iron status will be altered during acute HA exposure after PIO administration compared to PLA.

B5. RESEARCH PLAN

B5.1 Research Design

This study will be a randomized crossover double blind placebo control trial.

Table 1: Study Timeline

Study Day	Baseline					Trial 1					Washout	Trial 2				
	SV	1	2	3	4	5	6	7	8	9		20	21	22	23	24
Medical Screening	X															
Body Composition		X														
Height		X														
Weight		X								X						X
VO ₂ peak		X	X													
High Altitude Exposure			X							X						X
Practice Exercise				X	X											
Glycogen Normalization						X							X			

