Blood Sampling (credentialed procedure): Blood samples will be collected using an indwelling catheter kept patent using IV saline at approximately at approximately -300, -120, -30, 0, 20, 40, 60, 80, and 140 min during exercise by a USARIEM credentialed phlebotomist. Baseline blood sampling will occur after a 10-hr overnight fast on experimental trial days. A total of 18 blood samples will be completed during this study taking ~340 mL of blood sampled from each volunteer over the experimental trial days (**Table 3**). Blood samples will be used for isotope analysis assessment, substrate and hormone responses, and iron markers (**Table 3**).

For glucose kinetic analysis, the tracer/tracee ratio (6,6-[²H]₂] glucose/glucose) using gas-chromatography-mass spectrometry (GCMS; Metabolic Solutions, Inc., Nashua, NH) (24), while ¹³C/¹²C in plasma glucose will be measured using isotope-ratio mass spectroscopy (IRMS; Metabolic Solutions).

Breath Sampling (non-credentialed procedure): Breath samples will be collected at approximately -300, 0, 20, 40, 45, 50, 55, 60, 65, 70, 75, and 80 min during exercise to determine exogenous glucose oxidation using single-patient breath collection bags (Quin-Tron Instrument Company, Milwaukee, WI, USA). Baseline breath sample will also be collected prior to correct for background of naturally occurring ¹³C. The natural enrichment of the glucose ingested and the ¹³C/¹²C in expired gas samples will be analyzed using isotope-ratio mass spectroscopy (Metabolic Solutions, Inc., Nashua, NH).

B5.4 Data Collection

Table 2. Outcome Variables

Data Element/Variable	Source	Operational Specification
Anthropometric data	Direct measurement	Height, weight, body composition
Substrate oxidation	Blood and breath	Glucose turnover, carbohydrate, fat, and protein oxidation
Metabolic response	Blood	Substrate analytes, hormones, inflammation, iron status

Table 3. Blood Analytes

Analyte	Time points (min)								
	-300	-120	-30	0	20	40	60	80	140 ⁴
Glucose ¹	x	x	x	x	x	x	x	x	x
Insulin ²	x			x	x	x	x	x	x
Free fatty acids ²	x			x	x	x	x	x	x
Lactate ²	x			x	x	x	x	x	x
Glycerol ²	x			x	x	x	x	x	x
Norepinephrine ²	x			x	x	x	x	x	x
Epinephrine ²	x			x	x	x	x	x	x
Hemoglobin ¹	x			x				x	
Hematocrit ¹	x			x				x	
¹³ C-glucose ³				x	x	x	x	x	x
6,6-[² H ₂] glucose ³		x	x	x	x	x	x	x	x
PBMC ¹	x			x				x	x
TNF α ¹	x			x				x	x
IL-6 ¹	x			x				x	x
IL-10 ¹	x			x				x	x
Hemooxygenase 1 ¹	x			x				x	x
Adiponectin ¹	x			x				x	x
Erythropoietin ¹	x			x					

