5.7.1.3 Any device not approved by the FDA

N/A

B5.7.2 Drugs

B5.7.2.1 FDA-approved and used in accordance with the approved labeling

B5.7.2.2 FDA-approved and used in a manner not in accordance with its approved labeling
Pioglitazone, Thiazolidinedione, Takeda Pharmaceutical Company

B5.7.2.3 Any drug not approved by the FDA

N/A

B8 Statistical Analysis

B5.8.1 Sample Size Estimation

Based on results of exogenous carbohydrate oxidation and MCR rate between SL and HA in our previous investigation (3, 4), a sample size of 8 is required to achieve 80% power (**Table 4**). We will request to enroll up to 24 individuals to account for withdrawals from the study.

Table 4: Previous study effect sizes

Study	Outcome	Delta	Effect Size	Sample Size
Young et al. (4)	Exogenous Glucose Oxidation	0.35 ± 0.21	1.11	7
Margolis et al. (3)	Exogenous Glucose Oxidation	0.09 ± 0.06	0.95	8
Margolis et al. (3)	MCR	3.1 ± 2.0	0.98	7

B5.8.2 Data analysis

Statistical analyses will be conducted using either SPSS (IBM Corp. Armonk, NY), SAS 9.3 (SAS Institute Inc., Carey, NC), or equivalent. Shapiro Wilks will be used to assess all data for normality. Data that are not normally distributed will be log transformed for statistical analysis. Paired T tests will be used to assess effects of study arms (HA+PIO vs. HA+PLA) on chamber conditions (barometric pressure, temperature, and humidity), oxygen saturation, heart rate, $\dot{V}O_2$, $\dot{V}CO_2$, respiratory exchange ratio, ventilation exchange, total glucose and fat oxidation, plasma glucose, muscle, and liver oxidation. Mixed Model repeated measures ANOVA will be used to assess the effects of condition, time, and their interactions for breath ^{13}C -enrichments, exogenous glucose oxidation, and blood analytes. Bonferroni adjustments for multiple comparisons will be performed if significant interactions are observed.

SECTION C: HUMAN RESEARCH PROTECTIONS

C1. RECRUITMENT AND CONSENT

C1.1 Identification and Selection of Subjects

Volunteers will be recruited from the federally and non-federally employed civilian population, the Natick Human Research Volunteer (HRV) Pool, NSSC active duty military personnel, and the active duty population located at other military organizations, to include, but not limited to coordination with the NSSC Soldier and Squad Optimization and Integration Team (SSO-IT).

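### Post-interaction Bonferroni is not limited to PIO-PLA contrasts; Holm's step-down on named matched times keeps the same family-wise error and never rejects less

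*Combined protocol and SAP*

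**What the plan says.** B5.1 sets the design: "This study will be a randomized crossover double blind placebo control trial". The three hypotheses in B4 each compare PIO with PLA; none compares one time with another.

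B5.8.2 gives the model for breath enrichment, exogenous glucose oxidation and blood analytes: "Mixed Model repeated measures ANOVA will be used to assess the effects of condition, time, and their interactions". The multiplicity plan is one sentence: "Bonferroni adjustments for multiple comparisons will be performed if significant interactions are observed". B5.8.2 gives no family, number of comparisons, alpha or sidedness, and leaves the software open.

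The sampling schedule in B5.3 determines how large a family can become. For breath: "Breath samples will be collected at approximately -300, 0, 20, 40, 45, 50, 55, 60, 65, 70, 75, and 80 min". Blood is drawn nine times per trial, with two to nine times per analyte in Table 3.

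B5.8.1 states that "a sample size of 8 is required to achieve 80% power", and derives this from sea-level against altitude contrasts: "Based on results of exogenous carbohydrate oxidation and MCR rate between SL and HA in our previous investigation".

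**The concern.** Two choices in the sentence work against a trial of eight completers.

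First, the family is open. After a significant interaction, the comparisons could be PIO-PLA at each matched time (about 10 for breath), or every pair of condition-by-time cells (153 or 276). They could also be the two conditions within each time, which is no adjustment at all. The first matches the hypotheses. The second spends alpha on contrasts such as PIO at 20 min against PLA at 75 min. The third leaves error across times uncontrolled.

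Second, single-step Bonferroni is the weaker of two simple procedures with the same error guarantee.

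At stake is the ability to say at which times PIO and PLA differ, and whether that answer depends on how the software call is written.

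**Working it through.** **The plan's own figure.** Table 4 lists effect sizes 1.11, 0.95 and 0.98 with N = 7, 8 and 7. Treating them as paired effects with 80% power:

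- one-sided 0.05, exact t: N = 7, 9, 8
- two-sided 0.05, normal approximation, (1.96 + 0.842)²/d² = 6.4, 8.7, 8.2: N = 7, 9, 9
- two-sided 0.05, exact t: N = 9, 11, 11

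The stated sizes are reproduced to within two by the first two methods, but not by the third. At n = 8 and d = 0.95, exact power is 78% one-sided and 64% two-sided. The plan does not present its 80% as power at a single time.

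**Power per time under Bonferroni.** Assumptions: paired t-test, n = 8, 7 df, two-sided 0.05. The critical value is c = t(1 − 0.05/(2m); 7), and power = P(|T| > c) with T noncentral t, noncentrality d√8. Setting power to 80% at m = 1 gives d = 1.156, so noncentrality = 1.156 × 2.828 = 3.27.

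Family sizes: ten breath times after the first drink (20 to 80 min), m = 10. All cell pairs of a 2 × 9 table: 18 × 17/2 = 153. All cell pairs of a 2 × 12 table: 24 × 23/2 = 276.

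| m | c | d = 1.156 | d = 0.95 |
|---|---|---|---|
| 1 | 2.36 | 80% | 64% |
| 4 | 3.34 | 52% | 35% |
| 5 | 3.50 | 47% | 31% |
| 10 | 4.03 | 34% | 21% |
| 153 | 6.52 | 5.8% | 2.8% |
| 276 | 7.18 | 3.6% | 1.7% |

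Table 4's second row has delta/SD = 0.09/0.06 = 1.5. If that SD is of paired differences (the plan does not say), power is 95% at m = 1, 60% at m = 10 and 10–15% for all pairs.

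**If contrasts use the mixed model's pooled error.** Assumed df are 7 × 9 = 63 to 7 × 19 = 133, recalibrated to 80% unadjusted (d about 1.00). Power is then 48–49% at m = 10 and 15–20% for all pairs.

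**Holm against Bonferroni on the same family.** Holm tests the smallest p-value at 0.05/m, the next at 0.05/(m − 1), and so on. It therefore rejects everything Bonferroni rejects, and sometimes more. Simulated share of true differences found (n = 8, m = 10, compound-symmetric paired differences with between-time correlation 0.5–0.9, effect 1.156 unless shown):

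| Pattern | Interaction significant | Bonferroni | Holm |
|---|---|---|---|
| One time differs | not tabulated | 34% | 34% |
| Last five times differ | nearly always | 34% | 38% |
| Linear rise to 1.156 at 80 min | about half to nearly all trials | 16% | 20–22% |
| Equal effect at all ten | about 5% | 34% | 45–48% |

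Across the time-varying patterns tried at this size, the gain is about 2 to 7 points. A larger rise that averages 1.156 and peaks at 1.156 × 80/56 = 1.65 (56 min being the mean of the ten times) gives about 10. Simulated family-wise error at m = 10 was at most 4.7% for Holm and 4.5% for Bonferroni.

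**The case against.** Bonferroni is valid. The rule touches only follow-up comparisons, and the hypotheses ask whether PIO differs from PLA rather than at which minute. The condition main effect carries no Bonferroni adjustment; with a constant effect of 1.156 its power was 84–96% in simulation. This stands, and it limits the point to a worthwhile improvement.

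A reader might infer that the plan cuts power from 80% to 34%, or to 4–6%. The documents do not support that. The 80% in B5.8.1 is for the study, and d = 1.156 exceeds every effect size listed in Table 4. Nothing says all cell pairs will be tested; that is one reading of an open sentence. For exogenous oxidation a 2 × 12 table is unlikely: the calculation is relative to pre-drink breath, and it needs carbon dioxide output, which B5.3 measures at only six times.

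A reader might also infer that Holm always brings the 11 to 14 point gain. That gain belongs to an equal effect at all times, which seldom produces the interaction that triggers the rule. Nor is an interaction assured because both arms start near zero: that argument needs pre-drink values in the model, which the plan does not specify.

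Finally, the change is not wholly free. Holm has no simple matching simultaneous confidence intervals, and B5.8.2 assesses time as well as condition, so within-arm changes should not be forbidden.

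**Conclusion.** The point holds as an improvement to the analysis. The post-interaction rule is not confined to the contrasts the hypotheses concern, and it uses a procedure that Holm matches or beats on any given family at the same family-wise error.

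The sizes above are conditional on an assumed effect, two-sided 0.05, and either separate 7-df tests or an assumed pooled error. Fixing the family is the larger gain only if all cell pairs would otherwise have been tested. If the team already intended matched PIO-PLA pairs, the benefit is Holm's few points and a count settled in advance. No conclusion about the overall PIO-PLA effect is at risk from this sentence.

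**What to change.** Replace the Bonferroni sentence in B5.8.2 with:

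*If the condition-by-time interaction is significant, PIO is compared with PLA at each matched post-drink exercise time at which that outcome is measured (for outcomes without exercise samples, at each scheduled time in Table 3), two-sided, with Holm's step-down adjustment across those times at family-wise alpha 0.05; within-arm comparisons between times are descriptive and outside this family.*

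On the current schedule this gives 10 times for breath enrichment, 4 for glucose, insulin and the other analytes drawn throughout exercise (20, 40, 60, 80 min), 1 for the inflammatory markers (80 min), and 2 for the iron markers (−300 and 0 min). Exogenous oxidation has up to 10, or 5 if restricted to breath times that coincide with gas-exchange measurements (20, 40, 50, 60, 75 min); the plan should say which. The 140-min normoxic draw falls outside the family; if the team wants it, or the 0-min inflammatory sample, it should be named before unblinding.

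Cost: one sentence, with no new volunteers, samples or procedures. The team gives up simple matching simultaneous intervals and multiplicity-adjusted within-arm time changes.
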